All personnel will be properly trained in the protocol and procedures expected of them. In addition, refresher training may be conducted, as needed. Training logs will be kept in the study regulatory binders.

Monitoring of the Study

The sites will perform self monitoring of this study.

Source Data

All source documents will be maintained in the research chart for each subject. In addition, electronic medical records (EMR) may also be utilized by the study facility. It is the practice of the research facility to allow EMR access to monitors or auditors, if requested.

Study Timetable and End of Study

Patient recruitment is expected to be completed within 2 years of initiating the study. Once the final patient has been recruited, follow-up will last for 2 additional years. The study duration is estimated at 4 years.

During the time of enrollment, patients will be seen every three months. This includes the 3 month visit, 6 month visit, 9 month visit, and 12 month visit. At the 12 month visit, patients will be given the opportunity to continue in the study for an additional 12 months. This would include the 15 month visit, 18 month visit, 21 month visit, and 24 month visit.

Data Management

All data will be recorded on preprinted case report forms (CRF) suitable for electronic data capture. The case report forms will be kept in the patient's research chart. The research charts will be stored in a locked, secure location. Data will be entered by qualified personnel at the conclusion of study.

Statistical Methods

Sample Size

This trial will be a pilot study. Outcome estimates will form the basis for assessing the feasibility of designing a future large and definitive trial. One hundred fifty patients in each study arm will be enrolled (300 total patients). Since each patient will receive 2 vein grafts, on average, there will be approximately 300 vein grafts in each group (600 vein grafts total). This sample size will be large enough to detect whether a clinically important difference exists in terms of vein graft patency between the groups, but small enough that subject recruitment can be performed in an expedient manner, likely within the first 24 months of the study.

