This trial will not be designed or powered as a definitive clinical trial. Based on several previously published clinical trials, it is anticipated that 10-20% of vein grafts will be documented as occluded at the 1-year time point after CABG. Should ticagrelor improve graft patency and reduce vein occlusion from 20% to 10%, power calculations suggest that this pilot trial will have 96% power to detect a significant difference ($P<0.05$) between the groups. Alternatively, if ticagrelor were to decrease the occlusion rate from 15% to 10%, the power will be approximately 58%.

Statistical Analysis

All study data will be collected in a blinded fashion during the course of the trial. At 1- and 2-years after surgery, the CT coronary angiograms will be read and interpreted by board-certified radiologists with expertise in cardiac CT imaging. The radiologists will be blinded to study treatment assignment. The data analysis will also be performed in a blinded fashion, with un-blinding at the conclusion of the analysis. Study outcomes will be compared on an intention-to-treat basis according to the randomization study-group assignment. Vein graft occlusion, the primary outcome of the study, will be compared between the two randomization groups using a Fisher's exact test. To account for within-patient correlation and the possibility of multi-graft occlusion within individual patients, vein graft data will also be analyzed using logistic regression fit with generalized estimating equations methods. For secondary outcomes, continuous data will be compared between the two groups using two-sided Student's t tests, two-sample Wilcoxon rank-sum tests, or ANOVA, and a Fisher's exact test will be used for categorical data. Time to major adverse cardiovascular event will be determined for the study groups using the Kaplan-Meier method, and groups will be compared with a log-rank test. In accordance with intention-to-treat analysis, clinical and safety data will be analyzed for all randomized patients in the study. This will include data collected

from subjects who have dropped out of the trial or who refuse postoperative CT coronary angiography (5% expected refusal).

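### The claim that the sample can detect a clinically important difference holds only for a fall from 20% to 10%, and the primary analysis names no effect estimate with an interval

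*Combined protocol and SAP*

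**What the plan says.** Under Statistical Methods, Sample Size, the combined protocol and SAP calls the trial a pilot with 150 patients per arm and, at two vein grafts each, about 300 grafts per arm. It says that "Outcome estimates will form the basis for assessing the feasibility of designing a future large and definitive trial". It then states without qualification that "This sample size will be large enough to detect whether a clinically important difference exists in terms of vein graft patency between the groups". No size is attached to that difference.

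The same section next disclaims being a definitive trial in design or power. It says "it is anticipated that 10-20% of vein grafts will be documented as occluded at the 1-year time point after CABG" and gives two power figures. For a fall from 20% to 10%, "this pilot trial will have 96% power to detect a significant difference ($P<0.05$) between the groups". For the smaller effect, "if ticagrelor were to decrease the occlusion rate from 15% to 10%, the power will be approximately 58" per cent.

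Under Statistical Analysis, the primary outcome is compared by Fisher's exact test on grafts. Graft data are also analysed by logistic regression with generalized estimating equations (GEE) to allow for within-patient correlation. Expected refusal of CT angiography is 5%. The section names no effect measure, confidence interval or way of reading a non-significant result for the primary outcome.

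**The concern.** A sample said to be able to detect whether an important difference exists implies that a negative result would also be informative. Whether that is so depends on the size of the difference, which is left open. One of the plan's two modelled effects, a one-third reduction inside its expected range, would be missed about 42% of the time by its own figure (100 - 58).

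The analysis text does not make up for this. The plan's stated product is estimates for sizing a later trial, yet the first analysis it names gives a graft-level P value that ignores clustering. After P>0.05, a reader could cite the adequacy sentence as evidence that no important difference exists, with no planned interval to show what the data leave open. The later trial would also need the control rate and the within-patient correlation, and neither is listed as an output.

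**Working it through.** **Inputs.** From Sample Size: 300 grafts per arm, two per patient, expected occlusion 10-20%, effects of 20% to 10% and 15% to 10%, P<0.05. From Statistical Analysis: 5% CT refusal, giving 0.95 × 300 = 285 grafts per arm. Assumed, because the documents give no value: within-patient correlation r of 0.2-0.4.

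**1. The plan's power figures.** With grafts treated as independent,

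power = Φ{ [|p1 - p2| - z·√(2p̄(1 - p̄)/n)] / √[(p1(1 - p1) + p2(1 - p2))/n] }.

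- 15% vs 10%, n = 300: the two standard errors are 0.0270 and 0.0269. With z = 1.645, (0.05 - 0.0444)/0.0269 = 0.21, so power is 58.2%. With z = 1.960, (0.05 - 0.0529)/0.0269 = -0.11, so power is 45.7%.
- 20% vs 10%, n = 300: the two standard errors are 0.0292 and 0.0289. Power is 96.4% with z = 1.645 and 93.1% with z = 1.960.

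Both printed figures therefore match a one-sided 5% test on independent grafts. The plan does not state the sidedness of the primary test. Two-sided exact Fisher power is 41.1% and 92.0% at 300 grafts, and 39.4% and 90.5% at 285. The point below does not depend on this, because 58% is already the favourable figure.

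**2. The low end of the expected range.** For 10% halved to 5%, two-sided exact Fisher power is 59.3% at 300 grafts and 56.5% at 285.

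**3. Expected precision.** With the same occlusion p in both arms and two grafts per patient, the variance inflation is 1 + r and

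half-width = 1.96·√[2p(1 - p)(1 + r)/n].

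Example: p = 0.10, n = 300, r = 0 gives 1.96·√(0.18/300) = 4.8 points. Half-widths in percentage points:

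| Occlusion | Grafts per arm | r = 0 | r = 0.2 | r = 0.4 |
|---|---|---|---|---|
| 10% | 300 | 4.8 | 5.3 | 5.7 |
| 10% | 285 | 4.9 | 5.4 | 5.8 |
| 15% | 300 | 5.7 | 6.3 | 6.8 |
| 15% | 285 | 5.9 | 6.4 | 6.9 |
| 20% | 300 | 6.4 | 7.0 | 7.6 |
| 20% | 285 | 6.6 | 7.2 | 7.8 |

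**4. What a null result would exclude.** An observed difference of zero excludes a 5-point reduction only where the half-width is below 5. In the table that happens only at 10% occlusion with independent grafts. Even there the exception is narrow: (5/4.80)² - 1 = 0.08 and (5/4.93)² - 1 = 0.03, so a correlation of 0.08 (300 grafts) or 0.03 (285 grafts) removes it. A non-significant result that leans towards ticagrelor excludes less. With 15% vs 12.5% and 300 independent grafts per arm, the interval runs from -3.0 to +8.0 points in favour of ticagrelor.

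**The case against.** The strongest reply is that the plan is candid. It calls the trial a pilot, disclaims definitive power directly after the adequacy sentence, and prints the 58% in the same section. It never calls 15% to 10% clinically important, and for 20% to 10% the sentence is sound: 96% as stated, and 90-92% by two-sided Fisher. All of this stands. A reader might infer that the 58% figure contradicts the adequacy sentence. The documents do not go that far, because a contradiction needs 5 points to be the important difference and the plan names none.

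A reader might also infer that a non-significant P value would decide whether development stops. The documents contain no go/no-go rule and say that estimates will inform the next trial.

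Finally, silence about a confidence interval does not show that none would be reported. Arm-level proportions come with any Fisher comparison, and a logistic GEE ordinarily yields an odds ratio with a robust interval. That is fair. However, the plan does not say which estimate is primary, and a logistic GEE does not directly give a risk difference. The disclosure of 58% also does not tell a reader how to interpret P>0.05.

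**Conclusion.** The adequacy sentence is broader than the plan's own figures allow. It is supported for a reduction of about 10 points from 20%, and unsupported for 15% to 10% (about 58% stated) and for 10% to 5% (57-59% by two-sided Fisher). With 10-15% occlusion in both arms, the interval would be about ±5 to ±7 points wide, so in most cases a null result would leave a 5-point difference open; the exception is 10% occlusion with independent or nearly independent grafts.

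The range of 4.8-5.9 points uses only the plan's inputs and independence. The range of 5.3-6.9 points rests on the assumed correlation of 0.2-0.4. Both use a normal approximation and exactly two grafts per patient. This is a matter of claim and reporting, not a flaw that invalidates the trial. It deserves correction because it governs what may be concluded from a non-significant result.

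**What to change.** In Sample Size, limit the adequacy sentence to a reduction of about 10 points from 20%. Add the expected precision: a 95% half-width of about 5-7 points, or up to about 8 at 20% occlusion with correlation 0.4, with the correlation labelled as an assumption. Say that smaller differences such as 15% to 10% may be missed, and that a non-significant result will be interpreted through the confidence interval.

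In Statistical Analysis, make the GEE-based treatment effect with a robust 95% confidence interval the reported primary result. Include a risk difference, by identity link or by marginal standardisation from the logistic model. Report the aspirin-arm occlusion rate and the estimated within-patient correlation for sizing the next trial. Fisher's test can stay as a supporting analysis.

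A fixed rule based on excluding 5 points should be added only if the sponsor adopts that margin as its own.

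The cost is some wording, a little extra analysis from a model already planned, and a less favourable stated claim. No patients or scans are added.

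### The stated power of 96% and 58% fits an undeclared one-sided z-test; the named Fisher's exact test at two-sided 5% gives about 92% and 41%, or 90.5% and 39% after the expected CT refusals

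*Combined protocol and SAP*

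**What the plan says.** All the relevant text is under Statistical Methods in the combined protocol and SAP.

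- **Sample Size, number of units.** There are 150 patients per arm, and the calculation counts grafts: "Since each patient will receive 2 vein grafts, on average, there will be approximately 300 vein grafts in each group".
- **Sample Size, adequacy.** "This sample size will be large enough to detect whether a clinically important difference exists" in vein graft patency between the arms. The section also calls the trial a pilot that is not powered to be definitive.
- **Sample Size, power.** For 20% versus 10% occlusion, "power calculations suggest that this pilot trial will have 96% power to detect a significant difference ($P<0.05$) between the groups". For the smaller effect, "if ticagrelor were to decrease the occlusion rate from 15% to 10%, the power will be approximately 58" per cent.
- **Statistical Analysis, primary test.** "Vein graft occlusion, the primary outcome of the study, will be compared between the two randomization groups using a Fisher's exact test". No sidedness is given.
- **Statistical Analysis, sidedness elsewhere.** It is named only for secondary outcomes: "continuous data will be compared between the two groups using two-sided Student's t tests".
- **Statistical Analysis, missing scans.** Some patients are expected to "refuse postoperative CT coronary angiography (5% expected refusal"). The power paragraph does not mention this loss.
- **Statistical Analysis, correlation.** A GEE logistic regression is added: "To account for within-patient correlation and the possibility of multi-graft occlusion within individual patients". No correlation value is given.

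**The concern.** The two power figures look too high for 300 grafts per arm at a conventional 5% level. The 15% versus 10% scenario shows it best, because its power is near one half and so changes quickly with the critical value. If the figures came from a one-sided calculation, they do not describe the analysis as a reader would understand it, since the plan nowhere declares a one-sided test.

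Two things are at stake. These figures are the only numerical support for the claim that the trial can detect a clinically important difference. At two-sided 5%, the smaller effect moves from better than even odds of detection to worse than even. Its 15% control rate is also the midpoint of the 10% to 20% one-year occlusion that the plan anticipates. Second, with sidedness unstated, P<0.05 for the primary outcome has no fixed meaning, and this needs settling before unblinding.

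**Working it through.** **Inputs, all from the plan.** Grafts per arm n = 300 (150 × 2). Level 0.05. Rates p1 versus p2 of 20% versus 10% and 15% versus 10%. Refusal 5%, so 300 × 0.95 = 285 scanned grafts per arm. Grafts are treated as independent except in step 5.

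**Step 1. Reproduce the stated figures.** For the pooled z-test without continuity correction, with p̄ = (p1 + p2)/2,

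power = Φ{ [ |p1 − p2| − z·√(2p̄(1 − p̄)/n) ] / √( [p1(1 − p1) + p2(1 − p2)]/n ) }.

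One-sided 5%, z = 1.645, n = 300:

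- 20% versus 10%: (0.10 − 1.645 × 0.02915)/0.02887 = 1.80, power 96.4%.
- 15% versus 10%: (0.05 − 1.645 × 0.02700)/0.02693 = 0.21, power 58.2%.

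Both match 96% and 58%. The uncorrected unpooled and arcsine versions agree (96.6% / 58.4% and 96.6% / 58.5%). With 285 grafts per arm the pooled version gives 95.7% / 56.4%, a worse fit, so the refusals do not appear to have been applied.

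**Step 2. Same formula, two-sided 5%, z = 1.960, n = 300.**

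- 20% versus 10%: (0.10 − 1.960 × 0.02915)/0.02887 = 1.48, power 93.1%.
- 15% versus 10%: (0.05 − 1.960 × 0.02700)/0.02693 = −0.11, power 45.7%.

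Among the two-sided methods tried at 300 per arm (pooled, unpooled and arcsine z; continuity-corrected z; chi-square with and without correction; Fisher), none exceeds about 46% in the second scenario.

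**Step 3. The named test.** Power of Fisher's exact test is the sum of the two-binomial probabilities of all outcome tables with P<0.05.

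| Test at 5% | Grafts per arm | 20% vs 10% | 15% vs 10% |
|---|---|---|---|
| Stated in the plan | about 300 | 96% | 58% |
| One-sided z | 300 | 96.4% | 58.2% |
| Two-sided z | 300 | 93.1% | 45.7% |
| Two-sided z | 285 | 91.9% | 43.8% |
| Two-sided Fisher | 300 | 92.0% | 41.1% |
| Two-sided Fisher | 285 | 90.5% | 39.4% |
| One-sided Fisher | 300 | 95.7% | 53.6% |
| One-sided Fisher | 285 | 94.8% | 51.5% |

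**Step 4. Size of the gap.**

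- 15% versus 10%: 58 − 45.7 = 12.3 points (two-sided z, 300); 58 − 41.1 = 16.9 (two-sided Fisher, 300); 58 − 39.4 = 18.6 (two-sided Fisher, 285).
- 20% versus 10%: 96 − 93.1 = 2.9; 96 − 92.0 = 4.0; 96 − 90.5 = 5.5.
- As a yardstick, two-sided Fisher first reaches 96% at 362 and 58% at 446 grafts per arm, against about 300 planned.

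**Step 5. Separate sensitivity, on an assumption not in the plan.** With 2 grafts per patient the design effect is 1 + ICC. For an assumed ICC of 0.1, 0.2 and 0.3, 285 grafts per arm count as about 259, 238 and 219 independent grafts. Two-sided z power is then 89%, 86% and 84% for 20% versus 10%, and 41%, 38% and 35% for 15% versus 10%. The finding does not depend on this step.

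**The case against.** The strongest reply has four parts.

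1. **The plan does not say that the primary test is two-sided.** The hypothesis and objectives are directional, and on a one-sided reading the figures are a correct z-test calculation. The gap of 12 to 19 points depends on the two-sided reading. This stands as a qualification: if one-sided was intended, Fisher's test with 300 grafts per arm falls short by only 96 − 95.7 = 0.3 and 58 − 53.6 = 4.4 points. But a directional hypothesis does not declare a one-sided test, and the named test does not give 58% under either reading.
2. **This is a pilot, and 58% was never offered as adequate power.** True, and 20% versus 10% stays above 90% on the corrected figures. That limits the consequence. It does not make a stated power right, and the same section still claims the sample is large enough to detect an important difference.
3. **The graft count is approximate.** It is, so the thresholds of 362 and 446 are only a yardstick. The gap in the second scenario is far larger than the difference between 285 and 300 grafts can explain.
4. **A restated Fisher power still assumes independent grafts.** This stands. Positive correlation within patients would also undermine the nominal 5% level of a graft-level Fisher test. The restated figures should carry that assumption openly.

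**Conclusion.** The concern holds. The stated 96% and 58% match a one-sided 5% uncorrected z-test on about 300 independent grafts per arm. That is the best fit found, not a proven derivation, and the plan declares no such test. For Fisher's exact test at two-sided 5%, power is 92.0% and 41.1% with 300 grafts per arm, or 90.5% and 39.4% with 285. The error is modest for 20% versus 10% and material for 15% versus 10%.

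The larger gap rests on reading the primary test as two-sided, which is conventional but not stated. What needs no such reading is that the sidedness is undeclared, that the named test does not deliver 58% either way, and that the expected refusals are not shown in the calculation. All the main figures assume independent grafts.

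**What to change.** Keep the sample size and change the wording in two places.

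- **Statistical Analysis:** state the sidedness and level of the primary Fisher's exact test; two-sided 0.05 is the conventional choice.
- **Sample Size:** replace the power figures with, for example: *With about 285 scanned vein grafts per arm (300 less 5% refusal), and assuming independent grafts, a two-sided Fisher's exact test at the 0.05 level has about 90.5% power for 20% versus 10% occlusion and about 39% for 15% versus 10%.* If a one-sided test was intended, declare it and give about 95% and 52% instead.
- **Add a sentence for the GEE analysis:** positive within-patient correlation lowers power further. Label any range as an assumption, for example ICC 0.1 to 0.3 with 2 grafts per patient and 285 grafts per arm: about 89% to 84% and 41% to 35% by two-sided z-test.

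The cost is a few sentences and less favourable stated power. No patients or procedures are added.

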Prior to trial enrollment, in the early postoperative period, patients will be treated with usual aspirin antiplatelet therapy (typically 325 mg daily) starting within 24 hours after surgery, in keeping with current clinical guidelines [41]. At the time of randomization following surgery, this standard aspirin treatment will be discontinued. Patients will be randomized into an aspirin group (Arm A - aspirin 81 mg bid) or a ticagrelor group (Arm B - ticagrelor 90 mg bid). The study capsules will be identical to ensure blinding. Medication administration and data collection will be performed in a double-blind manner, such that neither the patient nor the healthcare personnel will be aware of the medication assignment.

Recruitment and written consent will be performed either prior to surgery or within 5 days after surgery. This interval of time after surgery will enable subjects to recover from anesthesia and the occasional confusion associated with postoperative narcotic use, in order to provide informed consent. Randomization will occur following surgery. Patients who are requiring high levels of hemodynamic support (more than 2 inotropes) within 48 hours after surgery will not be randomized into the study. Patients requiring postoperative anticoagulation with warfarin will also not be recruited. Following surgery, the study medication will be administered daily via nasogastric tube (if patient is intubated) or orally, starting on postoperative days 1-5, for the duration of 1-2 years.

Treatment will continue for 1 year, at which time patients will undergo a CT coronary angiogram to assess graft patency. Patients will then be invited to continue participating in the trial for 1 more year with the same study treatment. A repeat CT coronary angiogram will subsequently be performed for another graft evaluation at the 2-year time point after surgery. Because cholesterol levels can impact postoperative graft patency, current clinical guidelines recommend lipid-lowering therapy after CABG to achieve low-density lipoprotein (LDL) levels <100 mg/dL [41]. As such, patients in this trial will undergo lipid level evaluation at baseline before surgery and every 3 months during study enrollment. This information will be made available to clinicians involved in the care of study subjects to facilitate modification of lipid-lowering therapy, as needed, in keeping

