Study analysis will be performed at the 1-year and 2-year time-points. The first analysis will be conducted when the last recruited patient has passed the 1-year time interval after surgery and has undergone CT angiography. The second analysis will be performed when all recruited patients have crossed the 2-year time-point after surgery.

Important Medical Procedures to be followed by the Investigator

Overdose

If an overdose on an AstraZeneca study drug occurs in the course of the study, then the investigators or other site personnel will inform appropriate AstraZeneca representatives within one day (i.e. immediately but no later than the end of the next business day) of when he or she becomes aware of it.

The designated AstraZeneca representative will work with the Investigator to ensure that all relevant information is provided to the AstraZeneca Patient Safety data entry site.

Pregnancy

Patients who are pregnant or seeking to become pregnant will be excluded from trial recruitment. All outcomes of pregnancy, should they occur, will be reported to AstraZeneca.

References

1. American Heart Association: Heart Disease and Stroke Statistics - 2011 Update. Circulation. 2011;123:e1-e192.
5. Bourassa MG. Fate of venous grafts: the past, the present and the future. J Am Coll Cardiol. 1991;17:1081-3.
6. Fitzgibbon GM, Kafka HP, Leach AJ, Keon WJ, Hooper GD, Burton JR. Coronary bypass graft fate and patient outcome: angiographic follow-up of 5,065 grafts

related to survival and reoperation in 1,388 patients during 25 years. *J Am Coll Cardiol.* 1996;28:616-26.

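### One un-blinding rule serves two analyses: the plan does not say whether codes open after the 1-year analysis, about 12 months before the last 2-year CT, or to whom

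*Combined protocol and SAP*

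**What the plan says.** **Un-blinding rule.** Statistical Methods, Statistical Analysis: "The data analysis will also be performed in a blinded fashion, with un-blinding at the conclusion of the analysis". This is the only sentence that links un-blinding to an analysis.

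**Two analyses.** The same section continues: "Study analysis will be performed at the 1-year and 2-year time-points". On the first: "The first analysis will be conducted when the last recruited patient has passed the 1-year time interval after surgery and has undergone CT angiography". On the second: "The second analysis will be performed when all recruited patients have crossed the 2-year time-point after surgery".

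**Calendar.** The timetable section (Study Timetable and End of Study) allows two years for enrolment and says of the period after it: "Once the final patient has been recruited, follow-up will last for 2 additional years". It puts the whole trial at four years.

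**Blinding elsewhere.**
- Overall Study Design says that "neither the patient nor the healthcare personnel will be aware of the medication assignment". It also says that patients who accept the extension stay on their allocated study treatment for the second year.
- Statistical Analysis says that data collection is blinded for as long as the trial runs, and that the radiologists reading the CTs do not know the assignment.
- Blinding and Procedures for Unblinding the Study restricts the unblinded logs to pharmacy staff. It requires the Principal Investigator's authorization to unblind a patient, and allows this when the information is essential to that patient's care.

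**Data entry.** Data Management places data entry at the end of the study.

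**The concern.** A rule that refers to a single analysis cannot be applied unambiguously when there are two. The first analysis meets its literal condition, and nothing reserves un-blinding for the second. Patients recruited in the later part of accrual would at that moment still be in their second year on blinded capsules, with the 2-year CT to come.

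Two-year vein graft occlusion belongs to the primary objective, and cardiovascular and bleeding events are recorded through year 2. The extension is voluntary. If patients or site staff learned individual assignments, capsule use and attendance at the 2-year CT could shift differently by arm, and blinded CT reading prevents neither. Some year-2 outcomes also depend on decisions by clinicians or patients: hospitalization for ischemia, coronary intervention, and minor bleeding, which is defined partly by interruption of study medication. Later recruits' year-2 data would then be partly unblinded while earlier recruits' data were fully blinded. A broken blind cannot be restored.

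**Working it through.** **Inputs**
- Recruitment period R = 24 months and follow-up of 24 months after the last patient (Study Timetable and End of Study).
- N = 300 patients (Sample Size).
- First analysis: last patient past 1 year and scanned. Second: all patients past 2 years (Statistical Analysis).
- Not given, so assumed and varied: accrual shape, lag L between the first-analysis trigger and the opening of codes, and extension uptake u.

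**1. The plan's own figure.** Duration = R + 24 = 24 + 24 = 48 months. This reproduces the stated 4 years.

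**2. The gap.** First-analysis trigger = R + 12 = month 36. Last 2-year CT = R + 24 = month 48. Gap = 48 − 36 = 12 months.

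**3. Patients still before the 2-year CT if codes open at month t.** A patient enrolled at month e is still before the 2-year CT when e + 24 > t, that is, e > t − 24. With t = R + 12 + L and uniform accrual:

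share = 1 − (t − 24)/R, which for R = 24 is (12 − L)/24

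| Lag L (months) | Codes open at month | Share | Patients of 300 (u = 100%) |
|---|---|---|---|
| 0 | 36 | 12/24 = 50% | 150 |
| 3 | 39 | 9/24 = 37.5% | about 113 |
| 6 | 42 | 6/24 = 25% | 75 |
| 9 | 45 | 3/24 = 12.5% | about 38 |
| 12 | 48 | 0% | 0 |

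**4. Other accrual patterns at zero lag.** For R = 24, the accrual time elapsed at the cut-off is f = 12/24 = 0.5.
- Linearly falling accrual: share = (1 − f)² = 25% (75 patients).
- Linearly rising accrual: share = 1 − f² = 75% (225 patients).
- Uniform accrual completed in 18 months: codes open at month 30, the cut-off is e = 6, and share = 1 − 6/18 = 67% (200 patients).

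**5. Uptake.** Each count is multiplied by u. For example, u = 50% at zero lag under uniform 24-month accrual gives 150 × 0.5 = 75.

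**6. How much of the extension is exposed.** In the zero-lag uniform case, the affected patients enrolled at months 12 to 24. They have 36 − e = 12 to 24 blinded months behind them, mean 18. On average 24 − 18 = 6 months would remain.

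**7. If codes open only after the second analysis** (month 48 or later), no patient is still before the 2-year CT.

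**8. Text side by side.** A literal reading, with codes opened after the first analysis, is incompatible with blinded collection for the whole trial and with a double-blind extension. Opening codes after the second analysis is compatible with both. The logs rule limits who may see assignments and provides for individual un-blinding, but does not address what happens when an analysis is finished.

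**The case against.** A reader might infer that about half the patients would finish the extension year unblinded. The documents do not support that. The un-blinding sentence does not name the first analysis, and the surrounding text fits a code opened only after the 2-year analysis. The sentence also concerns the data analysis: decoding group labels in a dataset does not by itself tell patients, sites or CT readers anyone's assignment. Nor are patient-level codes unprotected, because the pharmacy-only logs and the authorization requirement have no stated expiry at year 1. These points stand, and they make this an unresolved conflict in the plan rather than a demonstrated loss of blinding.

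A reader might also infer that the analysis dataset would in effect be open, because the protocol identifies Arm A as aspirin and Arm B as ticagrelor. No section says the dataset will carry those labels. Neutral codes are a sensible precaution, not the correction of a stated error.

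It is fair, too, that the first analysis waits for the last patient's 1-year CT. One-year occlusion, the time point used for the power calculation, is therefore fully collected before any un-blinding. The trial also calls itself a pilot, and the 2-year scans are to be read blind.

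What the objection leaves open is that no section reserves un-blinding for the second analysis, limits the 1-year release to group level, or says who may see it. The safeguards show an intention to keep the blind but do not say how it survives a finished, decoded 1-year analysis.

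**Conclusion.** The point holds as an ambiguity with a real conflict on its literal reading, not as proof that the extension would be unblinded. The 12-month gap follows directly from the stated timetable. The figure of about half is conditional: it needs patient-level codes to be opened at the first analysis, uniform 24-month accrual, no lag and full extension uptake. A realistic analysis lag reduces it, while back-loaded or faster accrual would raise it. Uptake is not stated, so the counts are for full uptake. Even in the exposed group, most of the 24 months would on average have been blinded. The consequence is confined to 2-year occlusion and year-2 clinical and bleeding events. This is a cheap improvement, worth making before the first analysis is run.

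**What to change.** Replace the un-blinding sentence in Statistical Analysis with text stating that:

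- patient-level codes stay sealed with the unblinded pharmacy staff until the last 24-month CT has been read and the 2-year data are locked, apart from the individual un-blinding that the protocol already allows;
- the 1-year analysis uses neutral group codes and is decoded at aggregate level only;
- patients, site staff, outcome assessors and CT readers remain blinded to individual assignment through month 24;
- named roles, and no others, may see 1-year results by arm before then.

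Also reconcile Data Management, which places data entry at the end of the study, with an analysis due about 12 months earlier.

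**Cost.** A few sentences and neutral codes in the dataset. No new role is needed for holding the codes, because pharmacy staff already hold them. Individual assignments reach the investigators about 12 months later. A residual risk remains: if aggregate 1-year results are released during the extension, they could still influence behaviour, which is why the plan should say who sees them.
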